6.5 Criteria for Treatment Discontinuation

In the absence of treatment delays due to adverse events, treatment may continue until one of the following criteria applies:

- Disease progression
- Intercurrent illness that prevents further administration of treatment
- Unacceptable adverse event(s)
- Patient decides to withdraw from study
- General or specific changes in the patient's condition render the patient unacceptable for further treatment in the judgment of the investigator

7.0 STUDY MEDICATION

Commercial supply of all drugs will be used.

7.1 Sorafenib

The sorafenib tablets are manufactured by Bayer HealthCare AG, Germany.

The 200 mg tablet formulation contains sorafenib and the excipients croscarmellose sodium, microcrystalline cellulose, hypromellose, sodium lauryl sulfate, magnesium stearate. The tablets have a film coating consisting of hypromellose, polyethylene glycol, titanium dioxide, and red ferric oxide. The formulation is presented as an immediate release (IR) dosage form, (i.e., the active

ingredient is allowed to completely dissolve under *in vitro* test conditions within a short period of time with no intention of delaying or prolonging dissolution The tablets have a salmon color in appearance, weigh approximately 350 mg each, and are 10 mm round in shape.

The active compound of sorafenib is 4-{4-[3-(4-Chloro-3-trifluoromethyl-phenyl)ureido]-phenoxy}-pyridine-2-carboxylicacidmethylamide-4 methylbenzenesulfonate, and its molecular weight is 637 Daltons.

Sorafenib will be given orally at two tablets (200 mgx2) twice daily.

Subjects will be instructed on the proper administration of sorafenib. Sorafenib tablets should be taken 12 hours apart, at approximately the same time each morning and evening. Sorafenib tablets should be taken without food, at least 1 hour before or at least 2 hours after a meal, and with up to 240 mL (approximately 1 cup or 8 oz) of water. Consumption of grapefruit and grapefruit juice should be avoided while receiving study drug. Missed/vomited doses will not be made up.

7.2 5-FU

7.2.1Description

5-FU is one of the most important drugs used in medical oncology today. It is the key antitumor agent for colorectal carcinoma and is commonly employed in other malignancies, including breast cancer, throat cancer, and upper gastrointestinal malignancies. 5-FU belongs to the class of 5-fluoropyrimidines. It is an analogue of the pyrimidine uracil. At the carbon 5 (C-5) position, a fluorine atom is substituted in place of hydrogen. The fluorine atom does not impede the activation of 5-FU to the nucleotide level, which is essential to the antitumor activity of these compounds.

Although the precise antitumor mechanism of 5-FU remains uncertain, two pathways are thought to be central to its activity in certain cancers. First, 5-FU is metabolized to 5-fluoro-uridine triphosphate (FUTP) and is incorporated into RNA. This interferes with RNA synthesis and function. Second, 5-FU is metabolized to 5-fluoro-2'-deoxyuridylate (FdUMP) and acts as a quasi-substrate for the enzyme thymidylate synthase in the conversion of dUMP and methyltetrahydrofolate to dTMP and dihydrofolate. This in turn reduces pools of available thymidylate synthase, leading to the depletion of dTMP and dTTP and the accumulation of dUMP and dUTP, thereby inhibiting DNA synthesis.

7.2.2Drug Administration

5-FU will be prepared per institutional standard and administered as a continuous IV infusion over 46 hours through a central venous port-a-cath on days 1 and 15. An ambulatory infusion pump will be given to each patient, and the chemotherapy cartridge will be changed every 2 weeks for each new administration of 5FU.

7.2.3 Storage and Stability

Store at room temperature and protect from light. Dark yellow color indicates decomposition. Inspect for precipitate; if found, agitate or gently heat in water bath. Filter ampules with aspiration needle (5 mcm). Compatible with D5W, 0.9% NaCl, D5LR. Stable in polypropylene syringes. Stable in PVC reservoirs for infusion pump for 12 days. May adsorb to glass surfaces. Stable in cellulose nitrate/acetate ester or Teflon filters.

7.3 Oxaliplatin

7.3.1Description

Oxaliplatin is a third-generation platinum compound with activity in colorectal cancer. Its chemical name is trans-1-diaminocyclohexane oxalaplatinum or cis-[oxalato(trans-1-1,2-diaminocyclohexane) platinum (II)].

Oxaliplatin is a white crystalline powder, slightly soluble in water and very slightly soluble in methanol but insoluble in ethanol or acetone. The pH of an aqueous solution of 2 mg/mL is between 4.8 and 5.7.

Oxaliplatin is presented in the form of a freeze-dried powder for infusion in vials containing 50 mg and 100 mg of oxaliplatin corresponding with the following formula:

	50 mg vials	100 mg vials
Oxaliplatin	50 mg	100 mg
Lactose monohydrate	450 mg	900 mg
Nominal volume of vial	36 mL	50 mL

The finished product is presented in the form of a white to off-white cake or powder contained in a clear glass vial, sealed with a rubber stopper and aluminum seal with a flip-over cover.

7.3.2 Drug Administration

The freeze-dried powder is reconstituted by adding 10 to 20 mL (for the 50 mg vials) or 20 to 40 mL (for the 100 mg vials) of water for injection or 5% glucose solution and then by diluting in an infusion solution of 250 mL or 500 mL of 5% glucose solution. Do not administer undiluted. Dispose of any reconstituted solution that shows evidence of precipitation. The reconstitution or final dilution must never be performed with a sodium chloride solution. Oxaliplatin is incompatible with sodium chloride.

Do not combine with alkaline medications or media which cause oxaliplatin to degrade. Do not administer simultaneously by the same infusion line; flush line after oxaliplatin administration. Do not use for the preparation or administration needles or intravenous infusion sets containing aluminum components (there is a risk of degrading oxaliplatin).

Oxaliplatin will be administered at a dose of 85 mg/m² intravenously as a 2 - 6 hour infusion on days 1 and 15 of each cycle.

Antiemetics should be prescribed by the treating physician as clinically indicated if a patient develops nausea and/or vomiting. It is recommended that patients receive ondansetron (Zofran) 16 mg IV or granisetron (Kytril) 10 mcg/kg IV +/- prochlorperazine (Compazine) 10 mg PO or lorazepam (Ativan) 1-2 mg PO or IV 30 minutes prior to oxaliplatin administration if clinically indicated. Alternatively, oral forms of these antiemetics may be used at the treating investigator's discretion.

7.3.3 Storage and Stability

Information on expiration dates of oxaliplatin will be supplied on a lot-by-lot basis. The compound may be stored as freeze-dried powder for 3 years at room temperature. Reconstituted solution may be stored in 5% glucose solution or water for injection in the original vial for up to 48 hours between 5° to 30° C. After dilution in 5% glucose solution for infusion, the shelf-life is 24 hours at room temperature.

7.4 Leucovorin

7.4.1 Description

Leucovorin calcium is commercially available in 50 mg, 100 mg, 350 mg vials for reconstitution.

Please refer to the package insert for complete product information.

7.4.2 Drug Administration

Leucovorin will be administered as an IV infusion over 2 – 6 hours either concurrently with oxaliplatin through a separate line, or after oxaliplatin administration if a second line is not available. This can also be administered by institutional standard of care procedure policy.

Leucovorin may be reconstituted with BWI or with sterile water for injection. Solutions should be further diluted in D5W, 0.9% Sodium Chloride, or Ringers solution for infusion over two hours.

7.4.3 Storage and Stability

Intact vials should be stored at room temperature and protected from light. Solutions reconstituted with bacteriostatic water for injection (BWI) are stable for at least 7 days at room temperature.

7.5 Supportive Care Guidelines

- 7.5.1 H2 blockers or proton pump inhibitors can be prescribed for all patients as clinically indicated.
- 7.5.2 Management of nausea and vomiting Antiemetics should be prescribed by the treating physician as clinically indicated if a patient develops nausea and/or vomiting.
- 7.5.3 Anticoagulants See exclusion criteria section.

7.5.4 Growth factors

Prophylactic use of a colony-stimulating factor (G-CSF or GM-CSF) is not permitted on this trial. Nonetheless, use of a colony-stimulating factor for the treatment of febrile neutropenia as per American Society of Clinical Oncology guidelines is permissible (Bennett et al. J. Clin Oncol 1996 Sep; 14(9):2511-2520). Use of erythropoietin (including Procrit and Aranesp) for treatment of disease or treatment-related anemia is permitted.

7.5.5 Anti-Hypertensives

Patients who develop hypertension while on sorafenib may be treated with antihypertensive agents at the investigator's discretion. Dose modification for Grade 3 or 4 hypertension is described in Section 6.0.

7.6 Medications to Avoid

- Avoid use of drugs that are known potent CYP3A4 inducers, including but not limited to carbamazepine, phenobarbital, phenytoin, rifabutin, rifampin, and St. John's wort. These drugs can decrease systemic exposure to sorafenib and should be avoided. For participants who discontinue sorafenib while on study, please note that the use of anti-emetic CYP3A4 inducers is allowed.
- Avoid use of drugs that prolong QTc. If these drugs must be used, monitor QTc closely at the discretion of the treating physician.

8.0 Correlative Studies

Please see Appendix C.

9.0 Study Calendar

	S	creening	5	Sorat	afenib Cycle 1			Cycle 2 and				Every 8	End of		
Study Wool	2	2	1	2WK L	ead-In	1	2	2	4	sub	seque	ent cy	cles	weeks	I reatment [®]
Informed	-3	-2	-1	1	2	1	2	3	4	1	2	3	4		
consent	Х														
History		Х		Х	Х	Х	Х	Х		Х		Х			Х
Weight		Х		Х	Х	Х	Х	Х		Х		Х			Х
Performance		Х		x	x	x	x	x		x		x			х
Status				Λ	~	~	~	~		~		~			X
Toxicity		Ň		X	X	X	X	Х		X		Х			X
Vital signs		Х		Х	Х	Х	Х	Х		Х		Х			Х
Physical exam		x		x	x	x	x	x		x		x			x
CBC w/diff		X		v1	x	X	x	X		x		X			
Platelets		X		×1	Y Y	x x	x x	x x		x		x x			
Limplusio		×		X	~		~	Λ				Λ			
PT-INR		A X		v1											
		x x		X ¹	V		X	V				X			
BUN				X ¹	X	X	X	X		X		X			
BUN		X		X ¹	X	X	X	Х		X		Х			
Creatinine		X		x1	X	Х	Х	Х		Х		Х			
Uric acid		X		X1		Х				Х					
Total Bilirubin		Х		x1	Х	Х	Х	Х		Х		Х			
Alk phos		Х		x1	Х	Х	Х	Х		Х		Х			
LDH		Х		x1	Х	Х	Х	Х		Х		Х			
Protein		Х		χ1	Х	Х	Х	Х		Х		Х			
Albumin		Х		x1	Х	Х	Х	Х		Х		Х			
AST/ALT		Х		x1	Х	Х	Х	Х		Х		Х			
Calcium, Phos		Х		χ1	Х	Х	Х	Х		Х		Х			
Amylase		Х		X1		Х				Х					
Lipase		Х		χ1		Х				Х					
AFP		Х		χ1		Х				Х					
Hepatitis BsAg, cAb, sAb	x ³														
Hepatitis C Ab	x ³														
EKG	X														
Pregnancy test (serum or urine)			X5												
Tumor Measurement	Х													x ²	X ²
C/A/P CT or MRI	X ⁴													X ⁴	X ⁴
Sorafenib				Х	Х	Х	Х	Х	Х	Х	Х	Х	Х		
mFOLFOX						Х		Х		Х		Х			
Correlative				X											
Studies ⁷				and D3		X		Х		X					

1. Screen assessments need not be repeated for lead-in period.

2. Baseline measurements of tumor by radiographic means should be completed within 21 days prior to treatment and should include full evaluation of the extent of metastatic disease. Assessments are repeated every 2 cycles (8 weeks). Responses must be confirmed after 4-8 weeks with repeat radiological scans.

3. Hepatitis B and C serology as listed in the study calendar must be obtained within 120 days of study enrollment.

4. If abdominal/pelvic CT scan or abdominal MRI are chosen as the radiographic means of tumor measurement, then the same test should be repeated consistently every two cycles (8 weeks). If chest CT or chest MRI are chosen as the radiographic means of tumor measurement, then the same test should be repeated consistently every 2 cycles (8 weeks).

5. Female patients of childbearing potential only, within 7 days of initiation of treatment.

6. Every 6 months thereafter

7. Circulating endothelial cells and plasma levels of growth factors will be assessed on Day 1 (prior to first dose of sorafenib later that day) and Day 3 of lead-in phase, and on C1D1, C1D15, and C2D1 of FOLFOX-Sorafenib, and, if available, at the time of progression (see Appendix C for details). The Day 3 correlative can be drawn on Day 3, 4, or 5. The Day 15 correlative can be drawn on Day 14, 15, or 16. The Day 29 correlative can be drawn on Day 27, 28, or 29. An optional posttreatment tumor biopsy will be obtained any time from Day 10 to Day 14 of the lead-in phase in patients who consent to a posttreatment tumor biopsy (see Appendix D for details).

8. 24 hr urine must be done for 2+urine

10.0 Evaluation of Response

All patients with measurable disease who have received the first cycle of treatment and had a tumor re-assessment will be considered evaluable for response. In addition, those patients who develop early progressive disease or who discontinue early from the study due to toxicity will also be considered evaluable for response. Patients on therapy for at least the first cycle of treatment will have their responses classified according to the definitions below.

Response and progression will be evaluated in this study using the international criteria proposed by the RECIST (Response Evaluation Criteria in Solid Tumors (RECIST 1.1) committee. Changes in only the largest diameter (unidimensional measurement) of the tumor lesions are used in the RECIST criteria.

10.1Definitions

Measurable disease - the presence of at least one measurable lesion. If the measurable disease is restricted to a solitary lesion, its neoplastic nature should be confirmed by cytology/histology.

Measurable lesions - lesions that can be accurately measured in at least one dimension with longest diameter \ge 20 mm using conventional techniques or \ge 10 mm with spiral CT scan.

Non-measurable lesions - all other lesions, including small lesions (longest diameter <20 mm with conventional techniques or <10 mm with spiral CT scan), i.e., bone lesions, leptomeningeal disease, ascites, pleural/pericardial effusion, inflammatory breast disease, lymphangitis cutis/pulmonis, cystic lesions, and also abdominal masses that are not confirmed and followed by imaging techniques, cystic lesions and lesions occurring within a previously irradiated area unless they are documented as new lesions since the completion of radiation therapy.

Target/Non-target Lesions - all measurable lesions up to a maximum of five lesions per organ and 10 lesions in total, representative of all involved organs should be identified as *target lesions* and recorded and measured at baseline. Target lesions should be selected on the basis of their size (lesions with the longest diameter) and their suitability for accurate repeated measurements (either by imaging techniques or clinically). A sum of the longest diameter (LD) for *all target lesions* will be calculated and reported as the baseline sum LD. The baseline sum LD will be used as reference by which to characterize the objective tumor. All other lesions (or sites of disease) should be identified as *non-target lesions* and should also be recorded at baseline. Measurements of these lesions are not required, but the presence or absence of each should be noted throughout follow-up.

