S-FOLFOX in HCC

Yes: New lesions are present. Note: If new lesions are present, the patient is considered to have progressive disease overall.

Overall Response

Overall response will be determined as tabulated below, based on the evaluation of target, non-target, and new lesions:

Target lesions	Non-Target lesions	New Lesions	Overall response
CR	CR	No	CR
CR	Incomplete response/SD	No	PR
PR	Non-PD	No	PR
SD	Non-PD	No	SD
PD	Any	Yes or No	PD
Any	PD	Yes or No	PD
Any	Any	Yes	PD

To be assigned a status of PR or CR, changes in tumor measurements must be confirmed by repeat assessments that should be performed no less than 4 weeks after the criteria for response are first met. Longer intervals as determined by the study protocol may also be appropriate.

In the case of SD, follow-up measurements must have met the SD criteria at least once after study entry at a minimum interval (in general, not less than 6-8 weeks) that is defined in the study protocol.

Every effort should be made to document tumor measurements and extent of disease, even after discontinuation of therapy, in order to classify patients for overall response as described above. Patients who do not have tumor response assessment due to rapid progression or toxicity will be considered as non-responders, will be included in the denominator for the response rate, and will be classified into one of the following categories:

- death attributed to disease progression
- deterioration attributed to disease progression
- death attributed to drug toxicity
- early discontinuation attributed to drug toxicity

Note: If a patient receives subsequent therapy before tumor progression is documented, the reason for changing therapy must be reported; reasons

include clinical progression, drug toxicity, or secondary therapy for maintenance of tumor response.

Duration of Overall Response

The duration of overall response is measured from the time measurement criteria are met for CR or PR (whichever status is recorded first) until the first date that recurrence or PD is objectively documented, taking as reference for PD the smallest measurements recorded since the treatment started. Patients who do not relapse will be censored at the day of their last tumor assessment.

Time to response

Time from date of initial treatment until first objective documentation of response.

Time to tumor progression

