14.2.2 Secondary Efficacy Variables

The secondary objectives are to assess the toxicity profiles of this regimen and the preliminary data on response rate and overall survival. Overall survival is defined as the time from study entry until death from any cause. Overall survival will be calculated using the Kaplan-Meier method, and confidence limits for survival estimates will be calculated using the Greenwood formula. Progression free survival is defined as the time from study entry until disease progression or death from any cause. Response rate is defined as the percentage of patients achieving either CR or PR. Duration of response is defined as the time interval from the initial response to the time disease progression is observed.

All categories of toxicity and complications of the treatment will be recorded. Toxicity and complications of the treatment will be assessed based on reports of adverse events, physical examinations, and laboratory measurements.

REFERENCES/BIBLIOGRAPHY

3. Llovet JM, Bruix J: Molecular targeted therapies in hepatocellular carcinoma. Hepatology 48:1312-27, 2008

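### Does the response rate lack a usable denominator because Sections 10.0, 10.2 and 14.2.2 describe the patients differently?

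*Combined protocol and SAP*

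**What the plan says.** Section 10.0 gives the main rule: "All patients with measurable disease who have received the first cycle of treatment and had a tumor re-assessment will be considered evaluable for response". It then extends the set: "those patients who develop early progressive disease or who discontinue early from the study due to toxicity will also be considered evaluable for response". A third sentence reads: "Patients on therapy for at least the first cycle of treatment will have their responses classified according to the definitions below".

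Section 10.2 has the only explicit mention of a denominator: "Patients who do not have tumor response assessment due to rapid progression or toxicity will be considered as non-responders", and these patients "will be included in the denominator for the response rate". Its four listed categories cover death or deterioration from progression, and death or early discontinuation from toxicity. It also asks that "Every effort should be made to document tumor measurements and extent of disease, even after discontinuation of therapy".

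Section 14.2.2 states: "Response rate is defined as the percentage of patients achieving either CR or PR". It names no analysis set and describes the aim as obtaining "preliminary data on response rate and overall survival".

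Sections 5.1.6 and 6.5 list further reasons for stopping: intercurrent illness, withdrawal by the patient, and investigator judgement. Section 5.2.3 calls for a tumor reassessment at the end of treatment. Section 14.1 plans 40 patients.

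**The concern.** No sentence states that the rate is divided by the Section 10.0 set, and the phrase in Section 14.2.2 could be taken to mean everyone entered. Two kinds of patient are not placed when they stop for a reason other than progression or toxicity:

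- **Group (a):** those who leave before completing the first cycle. They fall outside the Section 10.0 rule.
- **Group (b):** those past the first cycle with no scan. The first sentence of Section 10.0 leaves them out, the third says their responses will be classified, and no listed category fits them.

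Neither group is likely to contain confirmed responders, so leaving them out can in practice only raise the rate. If the choice were made after seeing the data, or turned on how an early exit was labelled, the reported rate could be flattered.

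**Working it through.** **The plan's own figures.** The documents give no target, precision or test for response rate. The 40 patients are sized for time to progression (median 5 against 7 months, one-sided 10%, 80% power). A single-arm exponential calculation needs (1.2816 + 0.8416)² / (ln 1.4)² = 4.508 / 0.1132 = 39.8 events, which agrees with 40. Nothing in it depends on the response denominator.

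**The sections side by side.**

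| Patient | Section 10.0 | Section 10.2 | Section 14.2.2 |
|---|---|---|---|
| First cycle received, re-assessed | in | in | in |
| Early progression or toxicity exit | in | in, as non-responder if unassessed | in |
| Other exit, before first cycle complete (a) | out | not mentioned | not addressed |
| Other exit, past first cycle, no scan (b) | out by first sentence | not mentioned | not addressed |

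No row has two sections giving opposite instructions on the denominator. Section 14.2.2 defines the numerator and leaves the set to Section 10.

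**Timing, from first sorafenib dose.** Each cycle is 28 days and follows a 14-day lead-in.

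- End of cycle 1: 14 + 28 = day 42 (week 6).
- First scheduled scan, end of cycle 2: 14 + 56 = day 70 (week 10).
- Earliest confirmation of a response first seen at that scan: 10 + 4 = week 14.

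A patient with no scan cannot be CR or PR. A patient who leaves before week 6 is very unlikely to have a confirmed response. The numerator is therefore effectively fixed, and only the denominator can move.

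The end-of-treatment scan brings a group (b) patient into the evaluable set. It does not bring in a group (a) patient unless it shows progression.

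**Size.** Rate = r / (40 − k), with r responders and k patients left out. The documents give neither, so both are assumptions. The protocol cites response rates of 8.2%, 14% and 18% for oxaliplatin-based regimens in this disease; 0.14 × 40 = 5.6, so r = 6 is the central case. Clopper-Pearson 95% intervals are in brackets.

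| r | k = 0 | k = 1 | k = 3 | k = 6 |
|---|---|---|---|---|
| 4 | 10.0% (2.8–23.7) | 10.3% (2.9–24.2) | 10.8% (3.0–25.4) | 11.8% (3.3–27.5) |
| 6 | 15.0% (5.7–29.8) | 15.4% (5.9–30.5) | 16.2% (6.2–32.0) | 17.6% (6.8–34.5) |
| 8 | 20.0% (9.1–35.6) | 20.5% (9.3–36.5) | 21.6% (9.8–38.2) | 23.5% (10.7–41.2) |

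- Smallest shift: 4/39 − 4/40 = 0.3 points.
- Largest shift: 8/34 − 8/40 = 3.5 points.
- Interval widths: about 21 to 30 points.

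A registered patient who never starts treatment is simply one more in k.

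**How many exits would matter.** For a 5-point shift, r / (40 − k) must reach r/40 + 0.05:

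- r = 4: 4/26 = 15.4%, so k = 14.
- r = 6: 6/30 = 20.0%, so k = 10.
- r = 8: 8/32 = 25.0%, so k = 8.

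That is 35%, 25% or 20% of the trial leaving for reasons other than progression or toxicity and without a qualifying assessment.

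**Which denominator is closer to the truth.** Suppose the true rate is 14% and 10% of patients leave for reasons unrelated to response (both assumed). The evaluable rate is 14.0%; the all-treated rate is 0.14 × 0.90 = 12.6%. In that case the stricter denominator understates activity. If exits are concentrated in patients who would not have responded, the evaluable rate overstates it. Neither is right in every case.

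**The case for a change.** The strongest case for a change rests on pre-specification rather than size. Section 14.2.2 does not refer to Section 10.0, so treating the evaluable set as the denominator is an inference. Two competent analysts could report different rates from the same data. The shift runs in one direction, and a patient's inclusion may hang on whether an exit is recorded as toxicity or as withdrawal. One sentence would settle it without touching treatment, visits or sample size.

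Much of this stands. The link between the sections is not written down, and patients who leave for other reasons are not placed. The end-of-treatment scan and the instruction to keep measuring after discontinuation reduce group (b), but they do not say how to count those who remain.

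Three things limit the objection. The set that 10.0 and 10.2 describe together is coherent and already counts the exits that would flatter the rate most, progression and toxicity, as non-responses. The apparent conflict over group (b) does not affect the numerator, since an unscanned patient cannot be CR or PR under either sentence. And once the numerator and denominator are reported, as in any account of a 40-patient single-arm study, a reader can convert one rate to the other.

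**Conclusion.** This is a minor wording gap that an analyst would fill sensibly, and the choice of denominator is a fair trade-off. The natural reading of Section 10 is the evaluable set; an all-treated denominator would also be acceptable. The difference is 0.3 to 3.5 percentage points, assuming 4 to 8 responders and 1 to 6 patients out of 40 left out, and that none of those left out is a confirmed responder. These figures compare two denominators and do not estimate bias. The shift is small beside intervals about 21 to 30 points wide. Response rate carries no hypothesis test, target or stopping rule, and the plan calls it preliminary. The primary time-to-progression analysis is unaffected. Following the plan as written would not give an unsound result, so no change is called for. The conclusion would weaken only if roughly a fifth to a third of patients left unassessed for reasons other than progression or toxicity, and nothing in the documents suggests that.
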